9.1. Systemic Medications

Certain systemic medications are known to have a higher likelihood to interfere with contact lens wear, chiefly by disrupting the tear film.

A summary of disallowed systemic medications is shown in Table 4. Subjects with a history of taking these medications will be allowed to enroll only if:

- The medications have been taken on a continual, routine basis for at least 1 month, and
- The subject has demonstrated successful contact lens wear during this time.

Or:

- The subject was taking the medication on a temporary basis and ceased taking that medication at least 2 weeks prior to signing the informed consent (this is considered sufficient time for the medication to have left the body prior to enrollment).

Or:

- The subject is a neophyte. Based on the investigator's assessment, the use of the medication(s) will not interfere with the subject's participation in the study or with their ability to successfully wear soft contact lenses.

Subjects with a history of taking medications listed in Table 4 on a long-term, routine basis for less than 6 months will not be allowed to participate in the study.

Table 4: Disallowed systemic medications

Class of Drug	Common Indication(s)	Common Examples
Estrogens (not including contraceptive medication)	Menopause, osteoporosis, vaginitis	Vagifem, Estrace, Climara, Vivelle-Dot, Premarin, Minivelle, etc.
Anticholinergics	Irritable bowel syndrome, Parkinson's disease, peptic ulcer, cystitis, nasal congestion, cold symptoms, overactive bladder, COPD	Bentyl, Spiriva, Atrovent, Hyosyne, Levsin, Symax Fastab, Symax SL, Homax SL, Cogentin, Transderm Scop, etc.
Beta-blockers	Hypertension, angina, heart attack, migraine, atrial fibrillation, adrenal cancer, essential tumor, glaucoma	Toprol XL, Lopressor, Tenormin, Propranolol, Timoptic, Trandate, Inderal LA, etc.
Psychotropics	Antipsychotic (schizophrenia, mania), antidepression, antiobsessive, antianxiety, mood stabilizer, stimulants (ADHD)	Zoloft, Celexa, Prozac, Lexapro, Effexor, Cymbalta, Ativan, Xanax, Desyrel, Wellbutrin, etc.

Clinical Study Protocol

Johnson & Johnson Vision Care, Inc.

Class of Drug	Common Indication(s)	Common Examples
Vitamin A analogs	Cystic acne	Isotretinoin

Examples of disallowed systemic antihistamines are given in Table 5. Subjects with a history of taking systemic antihistamines will be allowed to enroll only if:

- They have taken antihistamines continuously for at least 2 weeks, and
- They have demonstrated successful wear while taking the medication

Or:

- They stopped taking the medication for at least 2 weeks prior to enrollment.

Or:

- The subject is a neophyte. Based on the investigator's assessment, the use of the medication(s) will not interfere with the subject's participation in the study or with their ability to successfully wear soft contact lenses.

Table 5: Disallowed systemic antihistamines

Class of Drug	Common Indication(s)	Common Examples
Antihistamines	Allergic rhinitis, sedation, hives, allergic conjunctivitis, skin allergy, itching, motion sickness	Hydroxyzine, Promethagan, Phenadoz, Vistaril, Claritin, Zyrtec, Astepro, Astelin, Optivar, Allegra, Benedryl, etc.

10. DEVIATIONS FROM THE PROTOCOL

Investigator will notify study sponsor upon identification of a protocol deviation. Protocol deviations must be reported to the sponsor within 24 hours after discovery of the protocol deviation. The Investigator will report deviations per IRB/IEC requirements. All deviations will be tracked, and corrective actions implemented as appropriate.

If it becomes necessary for the Investigator to implement a deviation in order to eliminate an immediate hazard to the trial subject, the Investigator may implement the deviation immediately without notification to the sponsor. Within 24 hours after the implemented deviation, the Investigator must notify and provide the rationale to the Sponsor and, as required, the IEC/IRB.

If the deviation potentially impacts the safety of patient or changes the technical integrity of the study, then it must be reported to IEC/IRB. This is a "Major Deviation". Deviations that contradict the information contained in the Informed Consent/Accent forms will be considered Major Deviations.

Clinical Study Protocol **Johnson & Johnson Vision Care, Inc.**

Minor deviations have no substantive effect on patient safety or technical integrity of the study. They are often logistical in nature.

Protocol waivers are prohibited.

Table 6 lists examples of deviations that will constitute major and minor protocol deviations for this study.

Table 6: Examples of major and minor protocol deviations

Deviation category	Major deviation	Minor deviation
Out-of-window visit	Visit attended 2-4 days out of visit window defined in study procedures if subject did not meet per protocol wear time. Visit attended more than 4 days out of visit window defined in study procedures regardless of wear time compliance.	Visit attended 2 or fewer days out of visit window defined in study procedures. Visit attended up to 4 days out of visit window and subject has met wear time compliance.
Unanswered PRO questions	Not applicable.	For questionnaires where data where any PRO questions are unanswered (i.e., left blank).
Insufficient wear of study lenses	Not applicable.	Subject does not wear study lenses for at least 1 hour prior to attending a follow-up visit or subject does not wear study lenses for at least 8 hours on at least 10 days of a study lens wear period.

In the case of a major protocol deviation, the decision of whether or not the subject will be excluded from the Per-Protocol analysis population will be made at the time of cohort review.

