8. SUBJECTS COMPLETION/WITHDRAWAL

8.1. Completion Criteria

Subjects are considered to have completed the study if they:

- provided informed consent.
- they are eligible.
- have not withdrawn/discontinued from the study for any reason described in section 8.2.
- completed all visits through the final visit (visit 5).
- If all visits were completed but an additional visit is considered necessary for subject care, follow the requirements for unscheduled visits in section 7.3.

Clinical Study Protocol

Johnson & Johnson Vision Care, Inc.

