8.2. Withdrawal/Discontinuation from the Study

A subject will be withdrawn from the study for any of the following reasons:

- Subject withdrawal of consent.
- Subject not compliant to protocol (e.g., refusing any protocol specified procedure)
- Subject lost to follow-up.
- Subject no longer meets eligibility criteria (e.g. the subject becomes pregnant).
- Subject develops significant or serious adverse events necessitating discontinuation of study lens wear
- Subjects who have experienced a Corneal Infiltrative Event (CIE).
- Investigator's clinical judgment regarding the subject safety reasons (that it is in the best interest of the subject to stop treatment).
- Subject not compliant with study lens wear schedule
- Subject not successfully dispensed due to lack of efficacy and safety including poor vision, poor comfort or unacceptable fit.

For discontinued subjects, the Investigator will:

- Complete the current visit (scheduled or unscheduled).
- Complete the Final Evaluation, indicating the reason that the subject was discontinued from the study.
- Record the spherocylindrical refraction with best corrected distance visual acuity.
- Collect used test article(s) (worn or brought to the visit) from the subject and discard them, unless otherwise stated in section 7.2
- Collect all unused test article(s) from the subject.
- Make arrangements for subject care, if needed, due to their study participation

Additional subjects will not be enrolled if a subject discontinues from the study prematurely.

In cases where a subject is lost to follow-up, every possible effort must be made to contact the subject and determine the reason for discontinuation/withdrawal. The measures taken to follow up must be documented including two written attempts and a certified letter (or equivalent) as the final attempt.

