14.3. Analysis Populations

The following analysis populations will be defined and used in the analysis and presentation of the data.

Safety Population:

All subjects who are administered any test article excluding subjects who drop out prior to administering any test article. At least one observation should be recorded. Subjects will be analyzed as per treatment received.

Per-Protocol Population:

All subjects who successfully complete all visits and do not substantially deviate from the protocol as determined by the trial cohort review committee prior to database hard lock. Justification for the exclusion of subjects with protocol deviations from the per-protocol population set will be documented in a memo to file. See section 10 for definition and examples of major deviations.

Intent-to-Treat (ITT) Population:

All randomized subjects regardless of actual treatment and subsequent withdrawal from the study or deviation from the protocol. At least one observation should be recorded. Subjects will be analyzed as per randomized treatment.

Clinical Study Protocol

Johnson & Johnson Vision Care, Inc.

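### Section 8.2 requires withdrawal for a lens-wear shortfall that Table 6 grades as minor, and nothing says which governs

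*Combined protocol and SAP*

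**What the plan says.** Section 8.2 opens its list with "A subject will be withdrawn from the study for any of the following reasons" and includes "Subject not compliant with study lens wear schedule". The bullet names no hours or days and does not refer to Table 6.

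Table 6 puts insufficient wear in the minor column: a "subject does not wear study lenses for at least 8 hours on at least 10 days of a study lens wear period". The major column for that row is marked not applicable. Section 10 describes minor deviations as having no material bearing on patient safety or on the technical integrity of the study. Another row of the table makes a visit major under this condition: "Visit attended 2-4 days out of visit window defined in study procedures if subject did not meet per protocol wear time". That row takes for granted that a child short of wear time still attends and is graded.

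For the analysis, 8.1 counts as completers only subjects who "have not withdrawn/discontinued from the study for any reason described in section 8.2". Section 14.3 defines the per-protocol population as "All subjects who successfully complete all visits and do not substantially deviate from the protocol", and 14.5 runs the primary test on it. After Table 6 the text reads "In the case of a major protocol deviation, the decision of whether or not the subject will be excluded from the Per-Protocol analysis population" and leaves that decision to cohort review.

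**The concern.** Two sites facing the same shortfall can act differently and each can cite the protocol. One logs a minor deviation and fits the next lens. The other withdraws the child at Visit 3 or 4. The first child can stay in the primary analysis set and the second cannot. Cohort review can take a child out of the set, but it cannot supply visits that never took place.

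The decision is made after randomisation, by an investigator whom 5.2 says cannot be completely masked, and against a criterion with no threshold. Discontinued subjects are not replaced (4.3). The intention-to-treat sensitivity analyses in 14.7, which would use the data of withdrawn children, are both optional, and the multiple-imputation one also requires dropout above 15%. If withdrawal for short wear were related both to the lens and to acuity, the per-protocol difference would be a biased estimate of the difference in all randomised children.

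**Working it through.** **Does any passage settle the conflict?** Section 4.1 gives the same minimum as Table 6 (10 days, 8 hours a day), so a threshold exists, but 8.2 does not cite it. Steps 2.2 and 5.2 have sites record hours and days worn and check them against the schedule, and no step says what follows if the child falls short. Section 10 rules out waivers, so a site that reads 8.2 literally has no stated discretion. No passage sets precedence.

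**The plan's own figures.** Inputs from 14.2: SD 0.084 for both lenses, margin 0.05, two-sided 5%, correlation ρ of 0.3 or 0.5, 50 completers.

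SD of the paired difference = 0.084 × √(2(1 − ρ)), which is 0.0994 at ρ = 0.3 and 0.084 at ρ = 0.5. Noncentrality = (0.05 − true difference) / (SD of difference / √n), with n − 1 degrees of freedom and one-sided 2.5%. At n = 50 this gives 93.7% and 98.5% for a true difference of 0, and 79.7% and 91.0% for 0.01 (ρ = 0.3 and 0.5). All 12 powers in Table 8 are reproduced.

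**Loss of numbers only.** With a true difference of 0.01 and ρ = 0.3, power is 79.7% at n = 50, 78.0% at n = 48 and 75.2% at n = 45. These values subtract from the completer target. The plan enrols 75 and allows (75 − 50)/75 = 33% attrition. Enrolment is counted from consent (4.3), so screening failures also draw on that allowance, but 10% of 75 is about 7.5 children against 25.

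**Illustration of selection.** The documents give no short-wear rate, no rate of withdrawal for wear and no link between wear and acuity. The following inputs are therefore assumed: a share q of 5% to 10% withdrawn; their acuity on the affected lens d = 0.03 to 0.10 logMAR worse than in the children who stay; a true EMO-118 minus MiSight difference of exactly 0.05 in all children; n = 50(1 − q), rounded to 48 or 45. The mean among those who stay is 0.05 − q·d if shortfalls fall on EMO-118 and 0.05 + q·d if they fall on MiSight. For example, with q = 10%, d = 0.10 and shortfalls on EMO-118, the mean is 0.05 − 0.010 = 0.040.

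Chance of wrongly declaring non-inferiority:

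| Assumed case | ρ = 0.3 | ρ = 0.5 |
|---|---|---|
| Balanced across lenses, or unrelated to acuity | 2.5% | 2.5% |
| On EMO-118, q 5%, d 0.03 | 3.2% | 3.3% |
| On EMO-118, q 10%, d 0.10 | 9.7% | 11.9% |
| On MiSight, q 5%, d 0.03 | 2.0% | 1.9% |
| On MiSight, q 10%, d 0.10 | 0.4% | 0.3% |

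The rows with 10% and 0.10 are extreme. Withdrawals that cost later visits arise after period 1 or 2, and a given lens falls in those periods in 4 of 6 sequences. So 10% of all children is 10% / (4/6) = 15% of the children who wear that lens then. A deficit of 0.10 is a full line, in children who passed the 20/25 check at step 2.28.

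**Step 2.29.** The dispensing sheet asks habitual wearers for 5 days a week. Over 11, 14 and 17 days that is 7.9, 10.0 and 12.1 days (days × 5/7), so a child who follows it and returns on day 11 can miss the 10-day count. Under Table 6 this adds only minor-deviation entries.

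**The case against.** The best defence is that the two passages do different jobs. Table 6 grades deviations for reporting and for per-protocol review, while 8.2 lists reasons to stop participation. Table 6 is the more specific text on short wear, and 8.2 may be meant only for gross non-compliance. The synopsis also gives the wear schedule simply as daily wear, so the bullet could concern overnight use. These readings are possible. The modality reading is the weaker one, because steps 2.2 and 5.2 check the schedule by hours and days. Nothing in the text confirms either.

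Oversight counts too. Deviations reach the sponsor within 24 hours, monitors check that they are documented, and a withdrawal needs a recorded primary reason and notice to the study CRA (7.3). A discontinued child completes the current visit, so acuity on the lens in question can be available to an intention-to-treat analysis. Section 14.1 defers detail to a stand-alone SAP, which may settle these rules. Silent selective removal is therefore less plausible, but none of this says which rule a site should follow.

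A reader might infer from the upper rows of the table that the plan inflates its error rate to about 10% or 12%, or that it favours EMO-118. The documents do not support that. Every input to those rows is assumed, the MiSight rows move the other way, and Section 1.4 reports little difference between optical designs on high-contrast acuity, which makes a lens-specific deficit of a full line hard to defend. A reader might also infer that the trial becomes underpowered, but the enrolment allowance argues against it. Nor can one say that short wear is major only when the visit is out of window: Table 6 gives examples, and the definition in Section 10 makes any deviation that alters technical integrity major.

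**Conclusion.** The inconsistency is real and should be removed, at low severity. Section 8.2 makes withdrawal mandatory for short wear without a threshold, Table 6 calls the same event minor, and the outcome decides who is in the primary analysis set. That conclusion rests on the text alone. Whether it would bias the result, by how much and in which direction, cannot be known from the documents. If shortfalls are balanced across lenses or unrelated to acuity there is no bias and only some loss of numbers, which the surplus enrolment probably absorbs. The error rates show only what the assumed shares and acuity deficits would imply.

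**What to change.** Replace the wear bullet in 8.2 with: *A lens-wear shortfall is recorded as a deviation under Table 6 and is not by itself a reason for withdrawal; the subject continues to the next lens.* Leave withdrawal for safety, consent or the investigator's clinical judgement as it stands. Keep any per-protocol exclusion for wear with the cohort review committee already named in 14.3, before hard lock, and state that it decides without knowledge of lens assignment.

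The cost is a routine protocol revision submitted to the IEC/IRB, with no added visits, procedures or subjects. Some low-wear children will stay in the study and possibly in the per-protocol set, as Table 6 already implies. Other discretionary exits remain, such as clinical judgement in 8.2 and investigator approval at step 2.28, so this change closes the wear route only.

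Bringing step 2.29 into line with the 10-day, 8-hour count for all wearers is optional housekeeping.

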11. STUDY TERMINATION

The occurrence of one or more Unanticipated Serious Adverse Device Effect (USADE), or any SAE where the relationship to study agent cannot be ruled out, may result in stopping

Clinical Study Protocol

Johnson & Johnson Vision Care, Inc.

further dispensing of test article. In the event of a USADE or SAE, the Sponsor may unmask the treatment regimen for the subject(s) and will discuss this with the Investigator before any further subjects are enrolled.

The Sponsor will determine when a study will be stopped. The Principal Investigator always has the discretion to initiate stopping the study based on patient safety or if information indicates the study's results are compromised.

JJVC reserves the right to terminate the study at any time for any reason. Additionally, the IEC/IRB reserves the right to terminate the study if an unreasonable risk is determined. The study can be terminated by the Principal Investigator at the individual clinical site due to specific clinical observations, if in their opinion, after a discussion with JJVC, it is determined that it would be unwise to continue at the clinical site.

JJVC (and the IEC/IRB and DMC, if applicable) will evaluate all adverse events. If it is determined that an adverse event presents an unreasonable risk, the investigation, or that part of the investigation presenting the risk, will be terminated as soon as possible.

Should the study be terminated (either prematurely or as scheduled), the Investigator will notify the IEC/IRB and Regulatory Authority as required by local regulatory requirements.

12. PROCEDURE FOR HANDLING PRODUCT QUALITY COMPLAINTS

A Product Quality Complaint (PQC) refers to any written, electronic, or oral communication that alleges deficiencies related to the identity, quality, durability, reliability, safety, effectiveness or performance of test articles after they have been released for clinical trial use.

Potential complaints may come from a variety of sources including but not limited to subjects, clinical research associates (CRA), clinical operations managers (COM), medical monitors, and site personnel, etc. The following are not considered product quality complaints:

- Subject satisfaction inquiries reported via "Subjective Questionnaires" and "Patient Reported Outcomes (PRO)."
- Clinical test articles that are stored improperly or damaged after receipt at the investigational site.
- Lens replacements that occur due to drops/fall-outs.
- Damage deemed by clinicians or clinical staff to be caused by handling by the user, and not indicative of a quality deficiency (i.e. tears, rips, etc.), only in situations where there is no deficiency alleged by the subject.

Within 24 hours of site personnel becoming aware that a PQC has occurred, the PQC must be recorded in the EDC system, which will trigger an automatic email notification to the appropriate COM/CRA and Clinical QA representative. In cases where the EDC system in use is not configured to send automatic notifications or when an EDC system is not used, the COM/CRA is responsible for notifying Clinical QA upon discovery that a PQC has occurred.

Clinical Study Protocol

Johnson & Johnson Vision Care, Inc.

Upon receipt of the EDC notification, the COM/CRA will contact the study site to collect additional information which will include:

- Date the complaint was received/recorded in the EDC System (Date of Sponsor Awareness).
- Who received the complaint.
- Study number.
- Clinical site information (contact name, site ID, telephone number).
- Lot number(s).
- Unique Subject Identifier(s).
- Indication of who first observed complaint (site personnel or subject).
- OD/OS indication, along with whether the lens was inserted.
- Any related AE number if applicable.
- Detailed complaint description (scheduled/unscheduled visit, wear time, symptoms, resolution of symptoms, etc.).
- Eye Care Provider objective (slit lamp) findings if applicable.
- Confirmation of product availability for return (and tracking information, if available), or rationale if product is not available for return

Once a complaint is received, it will be assessed by the COM, CRA, or trained site personnel to determine if it is an Adverse Event/Serious Adverse Event (AE/SAE). If the complaint results in an AE/SAE, the COM/CRA, or trained site personnel will follow section 13 of this protocol. If the AE/SAE was potentially the result of a product quality related deficiency, these procedures also apply and will be executed in parallel.

In some cases, a PQC form may be generated in EDC by the site in error. In this event, the PQC forms will be marked “Intentionally Left Blank” or “ILB”. Justification for ILB must be documented.

13. ADVERSE EVENTS

13.1. Definitions and Classifications

Adverse Event (AE) – An AE is “any untoward medical occurrence, unintended disease or injury, or untoward clinical signs (including abnormal laboratory findings) in subjects, users or other persons, whether or not related to the investigational medical device.”

Note: This definition includes events related to the investigational medical device or the comparator, and to the procedures involved. For users or other persons, this definition is restricted to events related to investigational medical devices.¹

An AE includes any condition (including a pre-existing condition) that:

- a) Was not present prior to the study, but appeared or reappeared following initiation of the study.

Clinical Study Protocol

Johnson & Johnson Vision Care, Inc.

- b) Was present prior to the study but worsened during the study. This would include any condition resulting from concomitant illnesses, reactions to concomitant medications, or progression of disease states.
- c) Pregnancy must be documented as an adverse event and must be reported to the clinical monitor and to the Sponsor immediately upon learning of the event.

Serious Adverse Event (SAE) – An SAE is any adverse event that led to any of the following:

- Death
- Serious deterioration in the health of the subject that resulted in any of the following:
 - Life-threatening illness or injury
 - Permanent or persistent impairment of a body structure or a body function
 - Hospitalization or prolongation of patient hospitalization
 - Medical or surgical intervention to prevent life-threatening illness or injury or permanent impairment to a body structure or a body function.
 - Chronic disease
 - Fetal distress, fetal death or a congenital physical or mental impairment of birth defect.

Per ISO 11980, Serious adverse events are those events that result in, or have potential to cause, either permanent impairment of an ocular function or damage to an ocular structure, and may necessitate medical or surgical intervention.

Serious adverse events may include any hazardous, sight-threatening conditions occurring after exposure to test article, including but not limited to the following.

- a) A presumed infectious ulcer (defined as a progressive erosion of the corneal tissue).
Signs may include irregular focal infiltrates (> 1 mm); active lesions with raised edges; significant diffuse infiltration; anterior corneal to mid-stromal involvement; erosion with overlying staining; conjunctival and lid edema; anterior chamber reaction (iritis); severe bulbar and limbal redness. Symptoms associated with a presumed infectious ulcer (microbial keratitis) may include pain of rapid onset; severe redness; purulent or mucopurulent discharge; tearing; photophobia. For the purposes of reporting, a corneal ulcer which has *any* of the following characteristics should be considered in this category:
 - 1) central or paracentral location;
 - 2) penetration of Bowman's membrane;
 - 3) infiltrate > 2 mm diameter;
 - 4) associated with iritis \geq grade 2;
 - 5) associated with any increase in intraocular pressure;
 - 6) culture positive for microorganisms;
 - 7) increasing size or severity at subsequent visits.
- b) Any central or paracentral corneal event (such as vascularization) that results in permanent opacification.
- c) Any serious adverse ophthalmic events including hypopyon and hyphema.
- d) Any neovascularization within the central 6 mm of the cornea.
- e) The loss of two or more lines of visual acuity that fail to resolve.

Clinical Study Protocol

Johnson & Johnson Vision Care, Inc.

f) All cases of iritis.

Diagnoses and conditions that are considered Ocular Serious Adverse Events include, but not limited to:

- Microbial Keratitis (MK)
- Iritis (including cells in the anterior chamber)
- Permanent decrease in best spectacle corrected visual acuity equivalent to 2 acuity lines or greater
- Central Corneal Opacity
- Central Corneal Neovascularization
- Uveitis
- Endophthalmitis
- Hypopyon
- Hyphemia
- Penetration of Bowman's Membrane
- Persistent Epithelial Defect
- Limbal cell Damage leading to Conjunctivalization

Significant Adverse Events – are defined as events that are symptomatic and warrant discontinuation (temporary or permanent) of the contact lens wear or require medical treatment to maintain normal ocular health.

Per ISO 11980, significant but non-serious adverse events should include, but not be limited to:

- a) peripheral non-progressive non-infectious ulcers;
- b) all symptomatic corneal infiltrative events;
- c) all cases of corneal staining greater than or equal to grade 3;
- d) a temporary loss of two or more lines of best corrected visual acuity (for greater than or equal to 2 weeks);
- a) cases greater than or equal to grade 2 neovascularization;
- b) any ocular event that necessitates temporary lens discontinuation of greater than or equal to 2 weeks.

Diagnoses and conditions that are considered Ocular Significant Adverse Events that may occur during the study include, but not limited to the following:

- a) Contact Lens Induced Peripheral Ulcer (CLPU)
- b) Significant Infiltrative Events (SIE)
- c) Superior Epithelial Arcuate Lesions (SEALs)
- d) Other grade 3 or higher corneal findings, such as abrasions or edema
- e) Non-contact lens related corneal events - e.g., Epidemic Keratoconjunctivitis (EKC)
- f) Asymptomatic Corneal Scar

In addition to above identified serious and significant adverse events, below are examples of other diagnoses and conditions that may occur during the study. The classification of these adverse events should be based on the above-specified definitions.

Clinical Study Protocol

Johnson & Johnson Vision Care, Inc.

- a) Non-significant Infiltrative Event (NSIE), if it is < Grade 2, non-symptomatic, and does not require medication
- b) Contact Lens Papillary Conjunctivitis (CLPC)
- c) Superficial Punctate Keratitis (SPK)
- d) Conjunctivitis: Bacterial, Viral, Allergic
- e) Blepharitis
- f) Meibomianitis
- g) Contact Dermatitis
- h) Localized Allergic Reactions

Adverse Device Effect (ADE) – An ADE is an “adverse event related to the use of an investigational medical device.”

NOTE 1: This definition includes adverse events resulting from insufficient or inadequate instructions for use, deployment, implantation, installation, or operation, or any malfunction of the investigational medical device.

NOTE 2: This definition includes any event resulting from use error or from intentional misuse of the investigational medical device.¹

Unanticipated Adverse Device Effect (UADE) – Any serious adverse effect on health or safety or any life-threatening problem or death caused by, or associated with, the test article, if that effect, problem, or death was not previously identified in nature, severity, or degree of incidence in the investigational plan, Investigator’s Brochure or protocol, or any other unanticipated serious problem associated with the test article that relates to the rights, safety and welfare of subjects.

